Twenty-four eligible participants will be block-randomized 1 to 1 treatment (12 participants) and control (12 participants) groups. All participants will undergo endoscopy and those without endoscopic contraindications will be eligible. All treatment group subjects will undergo combined HAPC and ESG where APC is applied according to on-label use prior to the standard ESG technique for enhanced fibrosis along the site of the plications potentially providing an avenue for longer and more durable ESG while minimizing the associated complications. Control subjects will undergo traditional ESG alone. All participants will undergo a repeat upper endoscopy at 26 weeks (6 months) +/- 2 weeks to evaluate the durability of the endoscopic sutures. All subjects will undergo research MRI at baseline and 26 weeks +/- 2 weeks to evaluate and grade the durability of the created gastroplasty, gastric motility, and gastric accommodation. This specially developed MRI protocol at Mayo offers a gold standard in evaluating gastroplasty durability. Additionally, at both baseline and 26 weeks +/- 2 weeks, all patients will undergo gastric scintigraphy to evaluate and measure gastric emptying.

Endpoints Effectiveness

Primary:

- Assess durability of endoscopic plications and sutures 26 weeks (6 months) +/- 2 weeks post procedure between patients receiving HAPC/ ESG vs traditional ESG alone.

Secondary:

- %TBWL in the combined HAPC and ESG group compared to traditional ESG at 6 and 12 months.
- Assess the procedure safety.
- % Excess weight loss (EWL) at 6 and 12 months between both groups.
- Proportion with $\geq 25\%$ EWL at 6 and 12 months by randomized arm.
- % of patients in the combined HAPC and ESG group achieving $\geq 5\%$ TBWL at 6 and 12 months compared to ESG alone.
- % of patients in the combined HAPC and ESG group achieving $\geq 10\%$ TBWL at 6 and 12 months compared to ESG alone.
- Changes in quality of life assessed using standard validated questionnaires (IWQOL-lite and SF-36) at 6 and 12 months compared to baseline.
- Changes in depression assessed using PHQ-9 questionnaire at 6 and 12 months compared to baseline.

- Improvement/reduction of hunger and desire to eat evaluated using validated self-reported ratings of appetite based on a 100-mm visual-analogue scale at 6 and 12 months compared to baseline.
- Improvement in eating behaviors evaluated using the Three Factor Eating Questionnaire (TFEQ) at 6 and 12 months compared to baseline.

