- Improvement in obesity related comorbidities (blood pressure, fasting glucose, HbA1c, lipid panel, liver enzymes) at 6 and 12 months compared to baseline.
- Changes in gastric motility, volume, accommodation, and constructed gastroplasty on MRI at 6 months compared to baseline.
- Changes in gastric emptying evaluated by gastric emptying study at 6 months compared to baseline.
- Changes in liver biochemical panel, and glucose homeostasis parameters at 6 months compared to baseline between the two groups.

Safety

- The incidence, frequency, and severity of adverse events related to treatment with the device will be reported throughout the duration of the study.
- Goal is <5% rate of serious adverse events related to the device or procedure (as determined by the site PI). Serious adverse events will be classified in the Adverse Events table.

Study Setting

The study will be conducted at 1 US center, Mayo Clinic in Rochester, MN. The maximum enrollment will be limited to 24 participants. The expected enrollment period is 6 months.

Subjects

Participants will be adult patients (Ages 21 \geq and \leq 65) with a BMI \geq 30 and \leq 40 kg/m² that meet the eligibility criteria below. All eligibility criteria must be met at the time of randomization.

Inclusion Criteria

1. Age 21-65
2. BMI \geq 30 and \leq 40 kg/m²
3. Willingness to comply with the substantial lifelong dietary restrictions required by the procedure.
4. History of failure with non-surgical weight-loss methods.
5. Willingness to follow protocol requirements, including signed informed consent, routine follow-up schedule, completing laboratory tests, and completing diet counseling.

6. Residing within a reasonable distance from the investigator's office and able to travel to the investigator to complete all routine follow-up visits.
7. Ability to give informed consent.
8. Women of childbearing potential (i.e., not post-menopausal or surgically sterilized) must agree to use adequate birth control methods.

Exclusion Criteria

1. History of foregut or gastrointestinal (GI) surgery (except uncomplicated cholecystectomy or appendectomy).
2. Prior gastrointestinal surgery with sequelae, i.e. obstruction, and/or adhesive peritonitis or known abdominal adhesions.
3. Prior open or laparoscopic bariatric surgery.
4. Prior surgery of any kind on the esophagus, stomach, or any type of hiatal hernia surgery.

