5. Any inflammatory disease of the gastrointestinal tract including severe (LA Grade C or D) esophagitis, Barrett's esophagus, gastric ulceration, duodenal ulceration, cancer, or specific inflammatory disease such as Crohn's disease or celiac disease.
6. Potential upper gastrointestinal bleeding conditions such as esophageal or gastric varices, congenital or acquired intestinal telangiectasis, or other congenital anomalies of the gastrointestinal tract such as atresias or stenoses.
7. Gastrointestinal stromal tumors, history of premalignant gastric lesions (intestinal metaplasia), history of familial and non-familial adenomatous syndromes.
8. A gastric mass or gastric polyps > 1 cm in size.
9. A hiatal hernia > 4cm of axial displacement of the z-line above the diaphragm or severe or intractable gastro-esophageal reflux symptoms.
10. A structural abnormality in the esophagus or pharynx such as a stricture or diverticulum that could impede passage of the endoscope.
11. Achalasia or any other severe esophageal motility disorder
12. Severe coagulopathy.
13. Insulin-dependent diabetes (either Type 1 or Type 2) or a significant likelihood of requiring insulin treatment in the following 12 months or a HgbA1C \geq 9.
14. Subjects with any serious health condition unrelated to their weight that would increase the risk of endoscopy.
15. Chronic abdominal pain.
16. Motility disorders of the GI tract such as gross esophageal motility disorders, gastroparesis or intractable constipation.

17. Hepatic insufficiency or cirrhosis.
18. Use of an intragastric device prior to this study due to the increased thickness of the stomach wall preventing effective suturing.
19. Active psychological issues preventing participation in a life-style modification program as determined by a psychologist.
20. Patients unwilling to participate in an established medically supervised diet and behavior modification program, with routine medical follow-up.
21. Patients receiving daily prescribed treatment with high dose aspirin (> 81mg daily), anti-inflammatory agents, anticoagulants, or other gastric irritants.
22. Patients who are unable or unwilling to take prescribed proton pump inhibitor medication.
23. Patients who are pregnant or breast-feeding.
24. Patients currently taking weight-loss medications or other therapies for weight loss within the prior 6 months.

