25. Subjects with severe cardiopulmonary disease or other serious organic disease which might include known history of coronary artery disease, myocardial infarction within the past 6 months, poorly controlled hypertension, required use of NSAIDs.
26. Subjects taking medications on specified hourly intervals that may be affected by changes to gastric emptying, such as anti-seizure or anti-arrhythmic medications.
27. Subjects who are taking corticosteroids, immunosuppressants, and narcotics.
28. Symptomatic congestive heart failure, cardiac arrhythmia, or unstable coronary artery disease.
29. Pre-existing respiratory disease such as moderate or severe chronic obstructive pulmonary disease (COPD) requiring steroids, pneumonia, or cancer.
30. Diagnosis of autoimmune connective tissue disorder (e.g. Systemic lupus erythematosus, scleroderma) or immunocompromised.
31. Specific diagnosed genetic disorder such as Prader Willi syndrome.
32. Eating disorders including night eating syndrome (NES), bulimia, binge eating disorder, or compulsive overeating.
33. Known history of endocrine disorders affecting weight such as uncontrolled hypothyroidism.
34. At the discretion of the PI for subject safety
35. If minority inclusion population target of 10% has not been reached by the 90% enrollment mark (example 21 of 24 subjects), the remaining enrollments will be reserved for minority subjects (example 3 of 24 subjects).

TRIAL PROCEDURES

Informed Consent

Prior to being enrolled in the trial, study participants must consent to participate after the nature, scope, and possible risks of the trial have been explained and outlined in an understandable form to them per the requirements of the IRB. Participants are free to withdraw consent at any time.

After reading the Informed Consent Form (ICF) document, the participant must sign and date the latest approved version of the ICF before any study procedures are performed (electronic via compliant system such as DocuSign, or wet-signed copy prepared in Participant Tracking System (Ptrax). A copy of the signed consent document will be accessible for the participant, and the original signed consent form will be retained by the study team.

Where possible, “remote” visits such as via phone or video call will be acceptable across the schedule of events to streamline coordination efforts and adapt to any unexpected conditions such as isolation protocol.

Study Timeline

The study timeline is depicted in Figure 1.

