Figure 1. Study Flow Diagram

Screening and Eligibility assessment

Screening will be conducted by the investigator or the co-investigator and documented on the Investigator delegated/medically qualified team member intake form (conventionally known as PI Intake Form) and Screening Labs form. Screening must occur no more than 45 days prior to randomization.

Screening will include the following:

1. Sign informed consent form
2. Screening exam and intake by the investigator or co-investigator
3. Height, weight, and BMI; waist and hip circumference; vital signs (blood pressure and pulse)
4. Dietary screening intake and approval
5. Laboratory tests (after 8 hours fasting)
 - **CBC:** hemoglobin, hematocrit, white blood cell count, mean corpuscular volume, platelets
 - **Chemistry panel:** sodium, potassium, chloride, CO₂, BUN, creatinine, fasting glucose, fasting insulin, SGOT/AST, SGPT/ALT, alkaline phosphatase, total bilirubin, direct bilirubin, albumin, fasting lipids profile (total cholesterol, triglyceride, LDL cholesterol, HDL cholesterol), Ferritin, B12, C-reactive protein.
 - **Coag:** INR, PTT
 - **Urinalysis**
 - **HgbA1C**
 - **H. Pylori Breath Test.** **Patients with a positive h-pylori breath test will be treated and eradication must be confirmed with a stool antigen after treatment and prior to randomization**
 - **EKG** for all patients
 - **Urine pregnancy test** for women of child-bearing potential^a
 - **MRI** at baseline to evaluate gastric anatomy, gastric motility, and gastric accommodation.
 - **Gastric emptying scintigraphy** at baseline to evaluate gastric emptying. Gastric emptying scintigraphy will be conducted according to current Mayo Clinic Rochester clinical protocol.
6. Questionnaires
7. Psychological evaluation and approval: Study psychologists will use their standard clinical evaluations for bariatric interventions.

Within one week (7 calendar days) of completion of the screening tests, the PI will review the results and determine the participant's eligibility. The center will inform the participant of their screening results within 10 days of completing testing. Any abnormal lab results will be communicated to the participant by delegated personnel, and they will be required to notify their primary care provider (PCP) for any further action that may be necessary. All potential participants who qualify for randomization based on the initial

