Participants will proceed to a brief visit with the dietician to review the post-op liquid diet, and the procedure (ESG or HAPC/ESG) will be scheduled within 60 days of randomization.

Trial Intervention

Participants will report to the procedure suite within 60 days of randomization. Participants of child-bearing potential will be required to have a pregnancy test within 7 days of the scheduled ESG or combined HAPC and ESG. Participants taking medications for hypertension and/or type II diabetes will be instructed to notify their prescribing physician of their procedure and to discuss any necessary medication changes for the post-op period.

The ESG or combined HAPC and ESG will be conducted in Saint Marys Hospital at the Mayo Clinic in Rochester, Minnesota. Within two hours prior to the procedure, IV access will be obtained, IV hydration initiated, and a transdermal scopolamine patch placed for patients 65 years of age or younger (this will be removed in 24 to 48 hours after the procedure). Scopolamine can precipitate delirium in elderly patients, and hence we will avoid using them in patients older than 65 years of age. After Hybrid ESG or traditional ESG patient will be monitored for 24-48 hours to ensure patient is able to tolerate liquid diet and discharge timing is to be determined on individual basis per the site primary investigator.

Prior to ESG or combined HAPC and ESG, a standard upper endoscopy is performed to rule out any contraindications. All procedures will be done under general anesthesia with endotracheal intubation and utilizing CO₂ insufflation. During the procedure, IV hydration will be continued, and patients will be given the following: one dose of IV antibiotics (Zosyn, Ceftriaxone, or Ciprofloxacin), 8 mg of IV Zofran, and 8 mg of Decadron. A minimum of two liters of IV hydration (either normal saline or lactate ringers) should be administered in the perioperative recovery period before discharge. Sequential compression devices

(SCDs) will be used perioperatively to decrease the risk of deep vein thrombosis (DVT) and pulmonary embolism (PE).

Patients will be prescribed the following medications or equivalent after the procedure to manage expected post-procedural symptoms:

- Zofran 4mg rapid dissolving pills taken every 6 hours as needed for nausea for 7 days
- Phenergan 25mg suppositories taken twice daily as needed for nausea for 7 days
- Low dose liquid narcotic taken every 6 hours as needed for pain for 5 days

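### Endoscopic eligibility is checked only after randomisation, and patients who fail the check have no stated accrual category

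*Combined protocol and SAP*

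**What the plan says.** **Eligibility.** Study Design, General Description: "All participants will undergo endoscopy and those without endoscopic contraindications will be eligible". Subjects: "All eligibility criteria must be met at the time of randomization". Several exclusion criteria ordinarily need a direct view of the stomach or oesophagus, for example criterion 8: "A gastric mass or gastric polyps > 1 cm in size".

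**Screening.** Screening and Eligibility assessment: "Screening must occur no more than 45 days prior to randomization". Once the screening tests are complete, "the PI will review the results and determine" eligibility, and those who qualify are then given their assignment. Neither the list in that section nor the one under Screening & Enrollment contains an EGD.

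**Endoscopy.** Trial Intervention places the procedure within 60 days of randomisation and says: "Prior to ESG or combined HAPC and ESG, a standard upper endoscopy is performed to rule out any contraindications". The Schedule of Events shows EGD at the procedure visit and Week 26 only.

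**Analysis.** Section 8, Statistical Analysis, removes patients found to meet exclusion criteria between randomisation and intervention, provided that the reason is documented and has nothing to do with arm. Missing Data repeats the removal but asks only for documentation. Section 8.2.3 limits the modified intent-to-treat (mITT) set to patients who received the intervention.

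**Accrual.** Study Setting: "The maximum enrollment will be limited to 24 participants". Replacement of withdrawn subjects counts pre-procedure withdrawals in the target and leaves screen failures out. It then says that new patients are randomised until 24 have had a procedure.

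**The concern.** The order of events defeats the protocol's own rule. A criterion that only endoscopy can settle is meant to be met at randomisation, but endoscopy comes afterwards. Each patient who fails becomes a post-randomisation exclusion, which allocation after the EGD would have prevented.

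Two things are at stake. First, the analysis plan requires such exclusions to be unrelated to arm, but the Randomization section leaves research teams unblinded and no blinded person is named to judge this EGD. (For the Week 26 EGD, Trial Intervention does provide an external blinded reader.) Keeping the allocation out of the medical record does not help here, because that measure is aimed at follow-up care. Second, the protocol does not say whether such a patient is replaced, or whether the patient falls inside the enrolment cap.

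**Working it through.** **1. The plan's own figures.** Screening to randomisation is up to 45 days and randomisation to procedure up to 60. 45 + 60 = 105, which matches the window in the Schedule of Events footnote. Planned size is 12 + 12 = 24, with no power calculation. The EGD can therefore fall up to 60 days after allocation within window; the footnote allows for overrun. The length of the gap is not the point: one day would raise the same issue.

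**2. Timing.**

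| Step | Where stated | EGD result available? |
|---|---|---|
| Screening tests and investigator's decision | Screening and Eligibility assessment; Screening & Enrollment | No |
| Randomisation, when all criteria must be met | Subjects | No |
| Procedure session, within 60 days | Trial Intervention | Yes |

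History and the screening MRI can settle some criteria earlier. Polyp size, ulceration and oesophagitis grade ordinarily need direct view. The prose carries this conclusion. The tick marks in the Schedule of Events are weak evidence, because the table as read places some Week 26 tests under later weeks.

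**3. Analysis set.** A disqualifying finding at this EGD fits the exclusion sentences in Statistical Analysis and Missing Data, and exclusion 34 (investigator discretion for safety) covers findings not listed. The patient leaves the mITT set. The sensitivity analysis in Missing Data compares withdrawn with participating subjects, so it does not clearly include someone excluded on criteria.

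**4. Accrual category.** The General Description, read alone, suggests that an EGD failure is a screen failure. The Schedule of Events footnote puts randomisation after all screening assessments, which points the other way, and the counselling that follows randomisation is labelled post-enrolment. The readable text does not settle it. Figure 1, the flow diagram, could not be read for this review.

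**5. Size.** The documents give no EGD failure rate, so q below is assumed.

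- Chance of at least one failure among 24: 1 − (1 − q)^24
- Chance of two or more: 1 − (1 − q)^24 − 24q(1 − q)^23
- Mean number treated if failures are not replaced: 24(1 − q)
- Mean number randomised if replaced until 24 are treated: 24/(1 − q)

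| q (assumed) | 2% | 5% | 10% | 15% |
|---|---|---|---|---|
| At least one failure | 38% | 71% | 92% | 98% |
| Two or more | 8% | 34% | 71% | 89% |
| Mean treated, no replacement | 23.5 | 22.8 | 21.6 | 20.4 |
| Mean randomised, with replacement | 24.5 | 25.3 | 26.7 | 28.2 |

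The last row exceeds the cap of 24 if the cap counts randomised patients.

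**6. Imbalance.** With 12 per arm, independent Binomial(12, q) losses and no replacement, the arms end two or more apart with probability 4%, 14%, 29% or 38%. The variance of a difference in means is proportional to 1/n₁ + 1/n₂. For 11 v 9 against 10 v 10: (1/11 + 1/9)/(2/10) = 1.010, a rise of 1.0%. For 12 v 10 against 11 v 11: (1/12 + 1/10)/(2/11) = 1.008, a rise of 0.8%.

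**The case against.** The strongest reply is that this is a pilot with one endoscopy session by design, and that the plan already says what happens to a patient who fails. Statistical Analysis and Missing Data both name patients found to meet exclusion criteria before intervention, and exclusion 34 catches the remaining safety findings. The shorter wording in Missing Data does not cancel the conditions in Statistical Analysis. All of this stands: a reader might infer that the analysis of EGD failures is undefined, but the text largely defines it as exclusion on criteria. What stays open is the accrual category and coverage by the sensitivity analysis.

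A reader might also infer that the exclusions will be biased. The documents do not support that. The plan requires the reason to be unrelated to arm and the rule to be applied in both arms; if that is followed, no bias arises. The weakness is only that the judgement is made when the allocation may be known.

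A third tempting reading is that arm imbalance threatens the comparison. Step 6 shows that a gap of two patients costs about 1% in variance, and it arises only if failures are not replaced, contrary to the last rule in the replacement section. It is also fair to say that the failure rates are assumed and that moving the allocation means editing many sections. Neither removes the contradiction over timing or the conflict within the replacement section, both of which hold at any failure rate.

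**Conclusion.** The point holds as a contradiction to be reconciled and a cheap improvement in design. Endoscopic criteria cannot be verified by endoscopy at the time the Subjects section requires, and failures become post-randomisation exclusions judged without a named blinded assessor. The readable text gives these patients no accrual category. The replacement section conflicts with itself, and replacement can pass the cap of 24 if the cap counts randomised patients.

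At an assumed failure rate of 2% to 15%, at least one such loss has a 38% to 98% chance. Without replacement, the expected number lost runs from 0.5 (24 × 0.02) to 3.6 (24 × 0.15). These figures measure lost patients, not bias. The textual findings do not depend on the assumed rates. The accrual finding carries one caveat: Figure 1 could not be read.

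**What to change.** Release the REDCap allocation in the procedure session, only after the diagnostic EGD is clear. EGD failures are then screen failures before allocation, which the replacement section already leaves out of accrual. The matching edits are:

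- General Description and Subjects: endoscopic criteria are verified at that EGD, before allocation; the others at screening.
- Schedule of Events: add an Inclusion/Exclusion check at the procedure visit.
- Screening and Randomization: replace the sentence on receiving the assignment, and say who learns the allocation and when.
- Replacement of withdrawn subjects: one rule, 24 randomised after a clear EGD, consistent with the cap in Study Setting.
- Keep the present randomisation visit as a dated pre-procedure visit that anchors the existing 45-day and 60-day windows. Reconcile every sentence tied to randomisation, including confirmation of H. pylori eradication, without changing its clinical timing.

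The cost is one amendment touching several sections and a change of timing in REDCap. No visit or procedure is added. There are two downsides. Ablation equipment must be on standby for every case. Screening data can be 105 days old at randomisation instead of 45, or older if the overrun footnote applies; their age at treatment does not change.

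If the timing cannot move: give EGD failures one accrual category, resolve the replacement section, carry the conditions from Statistical Analysis into Missing Data, include these patients in the sensitivity comparison, and report EGD exclusions by arm with reasons. That costs wording and one table.
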